12.3 Analysis of Primary Endpoint of Phase I - Safety Assessment

The safety analysis will be performed in all treated subjects. AE data will be listed individually and incidence of AEs summarized by system organ class and preferred terms within a system organ class for each treatment group. When calculating the incidence of AEs, each AE (based on preferred terminology defined by CTCAE version 5.0) will be counted only once for a given subject. In analyses of grade and causality, if the same AE occurs on multiple occasions, the highest grade and strongest relationship to study drug will be assumed. If 2 or more AEs are reported as a unit, the individual terms will be reported as separate experiences.

Changes in vital signs, hematology and clinical chemistry parameters from baseline to the end of the study will be examined. Toxicity will be tabulated by type and grade. Toxicities will be characterized according to the CTCAE version 5.0. Treatment-emergent changes from normal to abnormal values in key laboratory parameters will be identified.

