3.3 Eligibility Criteria for Continuation in Study and Initiation of Immunotherapy

Patients must have eligibility checked prior to initiation of combination immunotherapy, and must meet the following criteria for continued participation in the study.

3.3.1 Patients must have received 8-16 14-day cycles of FOLFIRINOX-based chemotherapy (i.e. FOLFIRINOX, 5-FU/leucovorin, FOLFIRI). Patients may have received Gemcitabine/Abraxane due to intolerance of FOLFIRINOX, but cannot have switched chemotherapy regimens due to progression or lack of response.

3.3.2 Patients must have completed SBRT (recommend 6.6 Gy x 5 days) at Johns Hopkins Hospital.

3.3.3 All toxicities attributed to prior anti-cancer therapy other than alopecia, fatigue, and hematologic lab abnormalities must have resolved to Grade 1 (NCI CTCAE v5.0) or baseline before administration of study treatment.

Participants with toxicities attributed to prior anti-cancer therapy that are not expected to resolve and result in long lasting sequelae, such as neuropathy or alopecia after platinum-based therapy, are permitted to enroll.

3.3.4 ECOG performance status 0-1 (**Appendix A**).

3.3.5 Able to swallow pills or capsules and tolerate oral medication.

3.3.6 Adequate hematologic, renal, and liver function as defined below:

White blood cell count	$\geq 2,000 \text{ cells/mm}^3$
Absolute lymphocyte count	$\geq 500 \text{ cells/mm}^3$
Absolute neutrophil count	$\geq 1,000 \text{ cells/mm}^3$
Hemoglobin	$\geq 9 \text{ g/dL}^*$
Platelets	$\geq 80,000 \text{ cells/mm}^3^*$
AST and ALT	$\leq 3 \times \text{ULN}$
Total bilirubin	$\leq 1.5 \times \text{ULN}^{**}$
Serum creatinine	$< 1.5 \times \text{ULN}$ or creatinine clearance (CrCl) $> 40 \text{ mL/min}$ (measured using

A Phase I/II trial of combination immunotherapy with nivolumab and a CCR2/CCR5 dual antagonist (BMS-813160) with or without GVAX following chemotherapy and radiotherapy for locally advanced pancreatic ductal adenocarcinomas (PDACs)

the Cockcroft-Gault formula below):

$$\text{Female CrCl} = \frac{(140 - \text{age in years}) * \text{weight in kg} * 0.85}{72 * \text{serum creatinine in mg / dL}}$$

$$\text{Male CrCl} = \frac{(140 - \text{age in years}) * \text{weight in kg} * 1.00}{72 * \text{serum creatinine in mg / dL}}$$

- * Transfusion to achieve this level is not permitted within 2 weeks of Cycle 1 Day 1 of immunotherapy
- ** Subjects with Gilbert syndrome may proceed as long as total bilirubin <3.0 mg/dL.

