4.10 End of Treatment (EOT)

All subjects will return to the study site 30 days (± 7 days) after the last dose of study drug (or within 7 days prior to initiation of a new anti-cancer treatment, whichever comes first) for an EOT evaluation. Procedures and assessments performed at this visit and beyond should follow the respective guidelines described in **Sections 4.11 and 9** as appropriate.

A Phase I/II trial of combination immunotherapy with nivolumab and a CCR2/CCR5 dual antagonist (BMS-813160) with or without GVAX following chemotherapy and radiotherapy for locally advanced pancreatic ductal adenocarcinomas (PDACs)

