Laboratory abnormalities: Laboratory abnormalities present at the screening visit will be recorded as pre-treatment signs and symptoms. After study treatment administration, all grade 3 and 4 clinical laboratory results that represent an increase in severity from baseline will be reported as adverse events. A grade 1 or 2 clinical laboratory abnormality should be reported as an adverse event only if it is considered clinically significant by the investigator. Any laboratory abnormality that required the participant to have a study drug discontinued or interrupted or required the participant to receive corrective therapy will be reported.

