6.1 Definitions

6.1.1 Adverse Event (AE)

Adverse event is defined as any undesirable sign, symptom or medical condition occurring after starting the study drug (or therapy) even if the event is not considered to be related to the study. An undesirable medical condition can be symptoms (e.g., nausea, chest pain), signs (e.g., tachycardia, enlarged liver) or the abnormal results of an investigation (e.g., laboratory findings, electrocardiogram). Medical conditions/diseases present before starting the study treatment are only considered adverse events if they worsen after starting the study treatment (any procedures specified in the protocol). Adverse events occurring before starting the study treatment but after signing the informed consent form will not be recorded. Additionally, expected progression of the disease being studied will not be recorded as an adverse event. Abnormal laboratory values or test results constitute adverse events only if they induce clinical signs or symptoms or require therapy.

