6.1.3 Non-Serious Adverse Event

A non-serious adverse event is an AE not classified as serious.

Any significant worsening noted during interim or final physical examinations, electrocardiograms, X-rays, and any other potential safety assessments, whether or not these procedures are required by the protocol, should also be recorded as a non-serious or serious AE, as appropriate, and reported accordingly.

Non-serious Adverse Events are to be provided to BMS in aggregate via interim or final study reports as specified in the agreement or, if a regulatory requirement [e.g. IND US trial] as part of an annual reporting requirement.

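### Sections 6 and 6.1.1 disagree on whether an asymptomatic, untreated Grade 3-4 laboratory worsening is an adverse event; a smaller gap is that the normal-to-abnormal summary in 12.3 and 12.5 cannot show worsening from an abnormal baseline

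*Combined protocol and SAP*

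**What the plan says.** **AE rules for laboratory results.** The laboratory paragraph in Section 6 says that, after study treatment, "all grade 3 and 4 clinical laboratory results that represent an increase in severity from baseline will be reported as adverse events". For lower grades it says "A grade 1 or 2 clinical laboratory abnormality should be reported as an adverse event only if it is considered clinically significant" by the investigator. It also requires reporting of any abnormality that stopped or interrupted a study drug or needed corrective treatment. Section 6.1.1, which defines an AE, ends: "Abnormal laboratory values or test results constitute adverse events only if they induce clinical signs or symptoms or require therapy". It makes no exception by grade.

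**Where AEs are used.** Section 1.4.1 makes the frequency, type and severity of all AEs from Cycle 1 Day 1 a Phase I primary endpoint. Section 4.6 defines DLTs from AEs and lists Grade 3 or higher AST, ALT or total bilirubin elevation with no symptom condition.

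**Laboratory summaries.** Sections 12.3 and 12.5 share the same text: "Changes in vital signs, hematology and clinical chemistry parameters from baseline to the end of the study will be examined", then a CTCAE toxicity table by type and grade, then "Treatment-emergent changes from normal to abnormal values in key laboratory parameters will be identified". The highest-grade rule in these sections is written for repeated AEs, not for laboratory values.

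**Entry values.** Section 3.3 requires that toxicities of earlier treatment "other than alopecia, fatigue, and hematologic lab abnormalities must have resolved to Grade 1" or baseline, so haematologic laboratory abnormalities may persist. It admits AST and ALT up to 3 x ULN, bilirubin up to 1.5 x ULN, haemoglobin from 9 g/dL and platelets from 80,000.

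**The concern.** The two AE rules cannot both be followed for one class of result: Grade 3-4, worse than baseline, without symptoms and without need of treatment. Whoever codes the events must pick a rule, and the Phase I primary endpoint depends on the pick. On a literal reading so does DLT status, because Section 4.6 starts from AEs. The Phase II unacceptable toxicities in Section 4.7 are also largely AE-based, and they feed the halting rule in 12.5.

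The second matter is narrower. Patients reach immunotherapy after 8 to 16 cycles of chemotherapy and then SBRT, so abnormal values before the first dose are foreseeable. A value that is already abnormal cannot change from normal to abnormal. What is at stake is whether low-grade, reversible hepatic, renal or haematologic drift in these patients appears in any laboratory summary.

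**Working it through.** No figure in the plan is at issue, so the check sets the rules side by side.

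**Step 1: the two AE rules on the same result.** All results are taken as worse than baseline, with no interruption of study drug.

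| Result | Section 6, laboratory paragraph | Section 6.1.1 |
|---|---|---|
| Grade 3-4, symptoms or treatment needed | AE | AE |
| Grade 3-4, no symptoms, no treatment | AE | not an AE |
| Grade 1-2, judged clinically significant, no symptoms, no treatment | AE | not an AE |
| Grade 1-2, not judged significant, no symptoms, no treatment | not an AE | not an AE |

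The second row is the main conflict. The third row is a lesser conflict of the same kind.

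**Step 2: which rule the rest of the protocol assumes.** In 4.6, Grade 3 or higher AST, ALT or bilirubin stands alone, while the next item, Grade 2 AST or ALT, carries a symptom condition. The authors added that condition where they wanted it. Sections 4.6 and 4.7 also exempt brief, uncomplicated Grade 3 laboratory abnormalities, and amylase or lipase rises without pancreatitis. Those exemptions would be largely unnecessary if such results were not AEs. Both features fit Section 6.

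**Step 3: which transient shifts are caught.** Take baseline grade 0, 1 or 2 and any higher peak up to 4, with return to baseline. This gives 4 + 3 + 2 = 9 shifts. Each is assumed asymptomatic, untreated, without interruption and, if the peak is Grade 1-2, not judged clinically significant. Grade 2 baselines are an assumption for illustration.

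| Shift | Normal-to-abnormal listing | AE under Section 6 | AE under 6.1.1 |
|---|---|---|---|
| 0 to 1, 0 to 2 | yes | no | no |
| 0 to 3, 0 to 4 | yes | yes | no |
| 1 to 2 | no | no | no |
| 1 to 3, 1 to 4, 2 to 3, 2 to 4 | no | yes | no |

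- Counted as an AE: 6 of 9 under Section 6, 0 of 9 under 6.1.1.
- Caught by neither the listing nor AE reporting: 1 of 9 (1 to 2) under Section 6, 5 of 9 under 6.1.1.
- Shown by a table of baseline grade against worst post-baseline grade: 9 of 9 under either AE rule.
- Worsening within a grade from an abnormal baseline is caught by neither the listing nor, at Grade 1-2 without action, AE reporting. A grade shift table does not show it either.

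These counts describe types of shift, not how often they occur.

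**Step 4: weight of one patient.** Reclassifying one patient moves an AE rate by 1/6 = 16.7 points in a Phase I cohort of 6, 1/5 = 20.0 points in a Phase II arm of 5, and 1/12 = 8.3 points in the maximum of 12 Phase I patients. This is the effect per patient. The documents do not allow an estimate of how many patients would be affected.

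**The case against.** On the AE rules, the other side can say that the text largely settles the matter. Section 6 gives a specific, mandatory laboratory rule, 6.1.1 is a general definition, and 4.6 sides with Section 6. This stands as evidence of intent. It does not remove the contradiction, because 6.1.1 says that laboratory values are AEs only under its own two conditions.

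On the summaries, the objection is stronger, and most of it stands:

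- The toxicity table by type and grade sits in the laboratory paragraph, after a separate paragraph on AEs. It may well cover all graded laboratory values, which would close the grade-shift gap. The text does not say.
- Change from baseline to the end of the study may mean change over all visits. Section 4.10 says "All subjects will return to the study site 30 days" after the last dose, or sooner if new treatment starts, by which time a rise on drug may have recovered. But the plan does not equate that visit with the end of the study, and laboratory panels continue in clinical follow-up.
- Section 6 already captures Grade 3-4 worsening, clinically significant Grade 1-2 results and anything that prompts action. Section 6.1.3 adds "Any significant worsening noted during interim or final physical examinations" or other safety assessments.
- Section 5.2.3 refers dose-delay management to Appendix E, whose algorithms are not in the text available to me. If they interrupt dosing for a given rise, Section 6 requires that rise to be reported.
- With at most 12 + 15 = 27 patients and individual AE listings, a shift table is partly a matter of presentation.

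**Conclusion.** The conflict between Section 6 and 6.1.1 is an error as written. It is confined to results that cause no symptoms and need no treatment. Its size is 1/n per reclassified patient, with the number of such patients unknown.

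The shift summary is a cheap improvement, not an error. The gap is transient Grade 1-2 or within-grade worsening from an abnormal baseline that is not judged significant and prompts no action. It exists only if the toxicity table draws on reported AEs alone and the end-of-study change does not use intermediate visits.

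A reader might infer three stronger things that the documents do not support:

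- **That dose or stopping decisions are compromised by the shift summary.** None of the DLT, unacceptable-toxicity or halting rules uses it.
- **That asymptomatic Grade 3 hepatic DLTs will be missed.** Section 4.6 names them explicitly, and investigators would probably follow that list. What is unsettled is whether they count as AEs.
- **That most scheduled panels go unanalysed, or that a predictable number of patients lose their worsening.** The former requires a two-point reading that the plan does not state. For the latter, the documents give neither the share of patients with abnormal entry values nor the chance of an uncaptured rise among them.

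**What to change.** 1. **Section 6.1.1, last sentence.** Replace it with wording to this effect: abnormal laboratory values are AEs as set out in the laboratory paragraph of Section 6, that is, all Grade 3-4 results worse than baseline, Grade 1-2 results judged clinically significant, and any result that leads to interruption, discontinuation or corrective therapy.

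2. **Sections 12.3 and 12.5.** Replace the normal-to-abnormal sentence with a shift table for each haematology and chemistry parameter: baseline CTCAE v5.0 grade against worst post-baseline grade, shown separately for Cycle 1 and for Cycle 2 onward. Define baseline as the last value before the first immunotherapy dose, and treatment-emergent as any increase in grade. Naming the baseline matters because panels are also taken before chemotherapy, and Section 4.1 puts about 5 to 9 months between enrollment and study drug. Keep the change-from-baseline summary, since a grade table does not show worsening within a grade.

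The cost is one amended sentence in 6.1.1, new wording in two analysis sections, and a standard table from panels already scheduled. No visits or samples are added. Because enrollment has closed, Grade 3-4 laboratory results already recorded should be checked against the AE data under the chosen rule. The downside is slightly higher reported rates of laboratory worsening, some of it due to SBRT or surgery rather than study drug. The split by cycle limits that but does not remove it.

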12.4 Analysis of Primary Endpoint of Phase II - Immunologic Assessment

The evaluable populations for Phase II primary immunologic endpoint includes all subjects who completed one cycle of study combination immunotherapy.

CD8/OX40 and CD8/CD137 double staining will be performed by the sequential striping/staining multiplex IHC method of formalin-fixed, paraffin-embedded (FFPE) tissue slides,³⁵ and will be further developed into a more quantitative assay for endpoint analysis with the Perkin-Elmer-Vectra multiplex immunofluorescent staining method in the Tumor Microenvironment Core ([name]/[name]) of the Bloomberg-Kimmel Institute for Cancer Immunotherapy.

For each group, the rate of immune response will be estimated as the proportion of patients treated with nivolumab and a CCR2/CCR5 dual antagonist (BMS-813160) with or without GVAX who achieve immune response, defined as >80% increase of infiltration of CD8+CD137+ T cell density after the first immunotherapy cycle at the time of surgery or surgical evaluation if not a candidate) compared to baseline (prior to SBRT and after chemotherapy), together with the corresponding 95% confidence interval.

A Phase I/II trial of combination immunotherapy with nivolumab and a CCR2/CCR5 dual antagonist (BMS-813160) with or without GVAX following chemotherapy and radiotherapy for locally advanced pancreatic ductal adenocarcinomas (PDACs)

Furthermore, descriptive statistics for immune parameters in pretreatment tumor biopsy specimens and that in matched post-treatment tumor specimens will be computed. Percent change in the intratumoral immune parameters will be reported using descriptive statistics and displayed graphically. Comparison of primary immune parameters between pretreatment tumor biopsy specimens and matched post-treatment tumor specimens will be conducted using paired t-tests (or Wilcoxon signed rank tests if appropriate) and McNemar's tests for dichotomous or categorical variables, respectively.

12.5 Analysis of Secondary Endpoints – Phase II Safety Assessment

The safety analysis will be performed in all treated subjects. AE data will be listed individually and incidence of AEs summarized by system organ class and preferred terms within a system organ class for each treatment group. When calculating the incidence of AEs, each AE (based on preferred terminology defined by CTCAE version 5.0) will be counted only once for a given subject. In analyses of grade and causality, if the same AE occurs on multiple occasions, the highest grade and strongest relationship to study drug will be assumed. If 2 or more AEs are reported as a unit, the individual terms will be reported as separate experiences.

Changes in vital signs, hematology and clinical chemistry parameters from baseline to the end of the study will be examined. Toxicity will be tabulated by type and grade. Toxicities will be characterized according to the CTCAE version 5.0. Treatment-emergent changes from normal to abnormal values in key laboratory parameters will be identified.

We will monitor adverse events in phase II, and if we observe >33% unacceptable toxicities in the first 6 patients or any time afterwards in any arm, we will halt the enrollment pending safety evaluations. Specifically, we stop if:

Number of patients in the same arm with AE \geq	2	3
In number of patients in that arm between	2-6	7 - 9

The operating characteristics of the stopping rule for toxicity are shown below and are based on 5000 simulations:

Risk of AE	0.10	0.20	0.25	0.30	0.33	0.40	0.45
% of Time study stops	12.2%	37.8%	52.8%	65.3%	71.6%	83.7%	89.8%
Expected sample size	8.66	7.98	7.57	7.21	7.03	6.66	6.45

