After completion of SBRT, the patients will then be re-evaluated for eligibility for continuation in the study and must have LAPC based on NCCN Guidelines as determined by review of CT, PET, or MRI imaging at our institution. Patients who have developed metastatic disease are no longer eligible to continue in the study. If the patients remain eligible for continuation in the study after rescreening, they will be assigned or randomized to a study arm (depending on when they were enrolled).

Due to availability of BMS-813160, study enrollment was closed as of December 19, 2022. Patients randomized prior to this will continue receiving study treatment as planned until drug supply expires on July 31, 2023, then will continue to receive any remaining study cycles without BMS-813160. Any patients who were enrolled but not randomized prior to December 19, 2022 (i.e. those receiving chemotherapy) will be assigned to a new arm (Arm C).

In phase I, the combination immunotherapy consists of nivolumab, CCR2/CCR5 dual-antagonist (BMS-813160) and GVAX. In phase II, the first 10 patients will be randomized 1:1 between Arm A and Arm B. Remaining patients will be assigned to Arm C.

Arm A subjects receive nivolumab and BMS-813160, Arm B subjects receive nivolumab, BMS-813160, and GVAX, and Arm C patients will receive nivolumab and BMS-813160 for Cycle 1 (prior to surgery) and then nivolumab and GVAX for Cycles 2 and beyond.

After randomization or assignment to a study arm, subject will receive Cycle 1 of the combination immunotherapy. Cycle 1 lasts 28 days and will start within two weeks of completion of SBRT.

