4.8 Stopping Rules

We will be monitoring toxicity for each arm in the Phase II portion, and if we observe >33% unacceptable toxicities in any arm, we will halt the enrollment pending safety evaluations and consideration by Principal Investigator, IND Sponsor, BMS and Medical Expert Committee (MEC).

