12.2 Sample Size/Accrual Rate

Each year, approximately 250 patients with newly diagnosed locally advanced pancreatic cancer are seen at JHH. Approximately, 50% of these patients will potentially be enrolled in clinical trials.

Phase I: 3-12 patients (3+3 design with Nivo+GVAX+BMS-813160 at two dose levels, primary endpoint - safety).

Phase II: up to 15 patients (primary endpoint - immunologic)

The first 10 patients will be randomized 1:1 into two arms:

Arm A: *nivolumab*+ *BMS-813160*

Arm B: *nivolumab*+ *BMS-813160*+ *GVAX*

Up to 5 additional patients will be assigned to Arm C: *nivolumab* + *BMS-813160* in Cycle 1

Due to the availability of BMS-813160, the enrollment of Phase II Arm A and Arm B will close early before full accrual under the original protocol. An amendment is required to change the design of the phase II portion. The analysis plan is also changed accordingly. The primary endpoint remains to be immunologic response, defined in Section 12.1 above.

The analysis will be performed separately in two groups of patients receiving either *nivolumab*+ *BMS-813160* (Group 1), or *nivolumab*+ *BMS-813160*+ *GVAX* (Group 2). Group 2 will include patients treated with the triplet regimen at the RP2D during both Phase II and Phase I portion. We expect up to 10 patients in Group 2 (including 6 treated at the 300mg dose in Phase I and 5 patients in Arm B of Phase II). A rate of immune response of 5% or lower is not considered worthy of further investigation, whereas immune response rate of at least 30% is consider worthy of further study.

Group 1 will have 8, up to 10, patients treated with the doublet regimen during Phase II (including up to 5 patients in Arm A and 3 to 5 patients anticipated to be enrolled to Arm C who receive *nivolumab* + *BMS-813160* in Cycle 1 and *nivolumab* + *GVAX* from Cycle 2 and after). It allows us to make preliminary assessment of immune response.

The probability of events under different true immune response rate is as follow:

number of responders out of 8 patients	True response rate				
	0.3	0.25	0.2	0.1	0.05
>=1	0.943	0.900	0.832	0.570	0.337
>=2	0.745	0.633	0.497	0.187	0.057
>=3	0.448	0.321	0.203	0.038	0.006
number of responders out of 10 patients					
	0.3	0.25	0.2	0.1	0.05
>=1	0.972	0.944	0.893	0.651	0.401
>=2	0.851	0.756	0.624	0.264	0.086
>=3	0.617	0.474	0.322	0.070	0.012

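### The Phase II toxicity stopping probabilities in Section 12.5 were computed for 9 patients per arm and overstate stopping by about 4 to 18 points now that each arm has at most 5

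*Combined protocol and SAP*

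**What the plan says.** Section 12.5 states the Phase II safety rule in words: "if we observe >33% unacceptable toxicities in the first 6 patients or any time afterwards in any arm, we will halt the enrollment". Section 1.7 has the same criterion. Section 12.5 then makes it specific in a two-row boundary. The row "Number of patients in the same arm with AE" gives at least 2 and at least 3; the row "In number of patients in that arm between" gives 2-6 and 7-9. The performance of the rule follows: "The operating characteristics of the stopping rule for toxicity are shown below and are based on 5000 simulations". Neither the maximum arm size nor the first look used in those simulations is given.

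Section 4.8 states the rule with no minimum number of patients: "if we observe >33% unacceptable toxicities in any arm, we will halt the enrollment pending safety evaluations".

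Section 12.2, as amended, sets the arm sizes. For Arms A and B, "The first 10 patients will be randomized 1:1 into two arms", so 5 each. For Arm C, "Up to 5 additional patients will be assigned to Arm C", with 3 to 5 anticipated. It says the analysis plan was changed to match. Section 1.7 records that "study enrollment was closed as of December 19, 2022"; patients enrolled but not yet randomized by then go to Arm C.

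**The concern.** The stopping probabilities are the plan's only quantitative statement of how well each Phase II arm is guarded against excess toxicity. Two features show, before any calculation, that they belong to a larger design: the boundary runs to 9 patients, and every printed expected sample size (6.45 to 8.66) exceeds the largest arm now possible. A safety board or ethics committee reading Section 12.5 would credit the rule with more sensitivity than it has.

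The sections also differ on when the rule applies. Someone following Section 4.8 and someone following the Section 12.5 boundary could reach opposite decisions on the same early data.

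**Working it through.** **Inputs.** Boundary, seven risks, stated stopping percentages and stated expected sample sizes: Section 12.5. Arm sizes: Section 12.2. Patients are taken as independent with a common risk p, each outcome being known before the next patient enters.

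**Step 1: reproduce the printed table.** Take a maximum of 9, no stop before patient 6, at least 2 events at 6, and at least 3 at 7 to 9. With X the number of events in the first 6 patients:

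P(stop) = P(X ≥ 2) + P(X = 1)·P(at least 2 of the next 3) + P(X = 0)·P(3 of the next 3).

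At p = 0.33: 0.6422 + 0.2673 × 0.2548 + 0.0905 × 0.0359 = 0.714.

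E[N] = 6 + P(not stopped at 6) + P(not stopped by 7) + P(not stopped by 8) = 6 + 0.3578 + 0.3578 + 0.3287 = 7.04.

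| Risk | Stated stop % | Max 9, first look at 6 | Stated E[N] | E[N], first look at 6 | E[N], applied from patient 2 |
|---|---|---|---|---|---|
| 0.10 | 12.2 | 12.5 | 8.66 | 8.65 | 8.48 |
| 0.20 | 37.8 | 38.8 | 7.98 | 7.95 | 7.36 |
| 0.25 | 52.8 | 52.4 | 7.57 | 7.58 | 6.73 |
| 0.30 | 65.3 | 64.8 | 7.21 | 7.23 | 6.11 |
| 0.33 | 71.6 | 71.4 | 7.03 | 7.04 | 5.75 |
| 0.40 | 83.7 | 83.5 | 6.66 | 6.67 | 4.97 |
| 0.45 | 89.8 | 89.7 | 6.45 | 6.46 | 4.48 |

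Stopping probabilities agree within 1.0 point. With 5000 simulations the standard error near 0.388 is √(0.388 × 0.612 / 5000) = 0.007, so that gap is simulation noise. Expected sizes agree within 0.03. Applying the boundary from patient 2 leaves the stopping probabilities unchanged but misses the expected sizes. Other maxima fail: at p = 0.33, 8 gives 67.1% and 12 gives 75.3%. A maximum of 10 (assuming at least 4 events from patient 10) matches on stopping but gives expected sizes of 9.53 to 6.57 with a first look at 6.

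**Step 2: apply the printed boundary to the arms in force.** With n ≤ 5 only the 2-6 column can be reached, so

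P(cross) = 1 − (1−p)^n − n·p·(1−p)^(n−1).

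At p = 0.33:
- n = 5: 1 − 0.1350 − 0.3325 = 0.532
- n = 4: 1 − 0.2015 − 0.3970 = 0.401
- n = 3: 0.255
- E[N] for an arm of 5: 1 + 1 + 0.8911 + 0.7452 + 0.5985 = 4.23

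| Risk | Stated % | Arm of 5, % | Overstatement, points | E[N], arm of 5 | Crossed by patient 4, % | Arm of 3, % |
|---|---|---|---|---|---|---|
| 0.10 | 12.2 | 8.1 | 4.1 | 4.91 | 5.2 | 2.8 |
| 0.20 | 37.8 | 26.3 | 11.5 | 4.68 | 18.1 | 10.4 |
| 0.25 | 52.8 | 36.7 | 16.1 | 4.52 | 26.2 | 15.6 |
| 0.30 | 65.3 | 47.2 | 18.1 | 4.35 | 34.8 | 21.6 |
| 0.33 | 71.6 | 53.2 | 18.4 | 4.23 | 40.1 | 25.5 |
| 0.40 | 83.7 | 66.3 | 17.4 | 3.96 | 52.5 | 35.2 |
| 0.45 | 89.8 | 74.4 | 15.4 | 3.76 | 60.9 | 42.5 |

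The patient-4 column is also the result for an arm of 4. It matters for an arm of 5 because a crossing at patient 5 comes when no place is left to withhold.

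**Step 3: compare the wordings in an arm of up to 5.** Two events exceed 33% and also meet the boundary at every size from 2 to 5. The rules part only on one event among the first 1 to 3 patients. One of 1 (100%) and 1 of 2 (50%) exceed 33% under Section 4.8 but do not reach 2 events. One of 3 (33.3%) does so if 33% means 0.33, but not if it means one third. Taken literally with 1 of 3 counted, Section 4.8 halts an arm of 5 with probability 27.8% at p = 0.10 (1 − 0.9³ = 0.271, plus 0.729 × 0.01) and 73.2% at p = 0.33. Without 1 of 3, the figure at p = 0.10 is 21.3%. The boundary gives 8.1% and 53.2% at these two risks.

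**The case against.** A reader might infer that the rule can never fire, since the table assumes no stop before patient 6 and no arm reaches 6. The documents do not support that. The operative boundary in Section 12.5 begins at 2 patients and works in an arm of 5. The first look at patient 6 is nowhere stated as a rule; it is inferred from the expected sample sizes. The 0% result appears only if that simulation setting is imposed on a boundary that contradicts it.

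It can also be said that Sections 1.7 and 4.8 are summaries of the specific boundary in 12.5, and that the disagreement is narrow. That largely stands: Step 3 confines it to one event among the first 1 to 3 patients. In arms this small, though, that is where much of the decision lies.

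The practical reach is limited. Arms A and B were randomized before the closure date, so new figures cannot change their accrual. Other safeguards remain: removal from treatment for unacceptable toxicity (Section 4.9), prompt reporting of serious events (6.5.1), weekly safety meetings (11.2) and at least annual board review (11.3). All of this stands and limits the consequence, but none of it makes the printed probabilities apply.

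Finally, Arms A and C together would have 8 to 10 patients, close to the 9 in the table. But Section 12.2 pools arms for the immune-response analysis only, and the stopping rule is per arm. Pooling by Cycle 1 regimen would combine regimens that differ from Cycle 2 while toxicity is counted to the end of treatment. Adding Phase I patients to Arm B would also mix dose-limiting with unacceptable toxicities, which Sections 4.6 and 4.7 define differently.

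**Conclusion.** The point holds as an un-updated table, not as a calculation error: the printed figures are right for 9 patients per arm with no stop before patient 6, and wrong for every arm now in the plan. Under the printed boundary an arm of 5 crosses 8.1% to 74.4% of the time instead of 12.2% to 89.8%, an overstatement of about 4 to 18 points that is largest at risks of 0.30 and 0.33. Protection is reduced, not lost. For an Arm C of 3 patients the range falls to 2.8% to 42.5%.

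The figures assume independent patients, a common risk and outcomes known before the next patient enters. Section 4.7 counts unacceptable toxicities through the end of treatment, so late events would make crossing in time to affect accrual less likely than the patient-4 column shows. The choice of 9 and a first look at 6 is inferred from the fit, since Section 12.5 states neither.

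**What to change.** - Replace the Section 12.5 table with operating characteristics for arms of 3, 4 and 5, and state the maximum size and first look assumed. The values in Step 2 serve for the printed boundary; any other boundary needs its own.
- Show separately the probability of crossing before the arm is full. For an arm of 5 this is the patient-4 column, for an arm of 4 the arm-of-3 column, and for an arm of 3 it is p² (0.33² = 10.9%).
- Reconcile Sections 1.7, 4.8 and 12.5 into one statement that settles whether there is a minimum number of patients, what one event among the first 1 to 3 patients means, and whether 1 of 3 exceeds the limit.
- Reconcile the action, halting enrollment, with the December 19, 2022 closure, after which only assignment to Arm C remains. State what a crossing in Arm A or B leads to.

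The cost is amendment wording and one recomputed table. The stated stopping probabilities become less favourable.
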